8.8.2 Analysis of Secondary Efficacy Endpoints

8.8.2.1 BIOMARKERS OF COMPLEMENT ACTIVATION

Biomarkers of complement activation: sC5b-9, C3a, C3, Bb, C4a, functional assays for classical and alternative complement pathways will be summarized by visit. Absolute values, changes from baseline, and percent changes from baseline will be summarized. The summaries will be done on PD set. Plots over time for biomarker results for individual patients will be prepared.

8.8.2.2 CLINICAL RESPONSE AT WEEK 24

Clinical response at Week 24 will be summarized. Counts and proportions of clinical response will be reported. 95% Clopper-Pearson confidence interval (CI) for proportion of responders will also be presented. Additionally, clinical response results will be summarized for all visits similar to what was done for Week 24. Patients meeting intercurrent events (ICE), including use of prohibited medication (Plasma exchange – identified by manual review, Defibrotide – ATC code B01AX and manual review, , complement inhibitors – ATC code L04AJ) or withdraw from the study before Week 24 are considered as failures/non-responders at all the visits occurring after the medication/withdrawal. The number and percentage of patients who had an ICE and by ICE category will be presented as well. Medical review of the programmatically generated list of prohibited medications will be performed prior to interim analysis and final database lock.

In addition, investigator assessed response will be summarized per visit. Counts and proportions of response categories (clinical response, partial response, and clinical worsening) will be reported.

8.8.2.3 TMA RESPONSE AT WEEK 24

TMA response at Week 24 is defined as improvement in laboratory markers as follows:

- LDH < 1.5 x ULN **and**
- Platelet count ≥ 50*10^9/L (50 000/mm³) without transfusion support during the prior 7 days and
- ≥ 50 % reduction from baseline in rUPCR

TMA response will be analyzed in the same way as Clinical Response at Week 24 (see Section §8.8.2.2 for details).

8.8.2.4 OVERALL SURVIVAL AT DAY 100

Overall survival at Day 100 (days) is defined as survival from the day of TA-TMA diagnosis and will be analyzed using Kaplan-Meier model. Kaplan-Meier survival estimate at Day 100 and its 95% CI will be presented. Counts and proportions of patients with events and censored will be presented, together with estimates of median and quartiles obtained from the model. Kaplan-Meier curves will also be presented. Death for any cause will be considered an event, with the date of death defining the event date. Patients alive on the date of last contact will be censored on this date. Pegcetacoplan-withdrawn patients for which survival at Day 100 is unknown will be censored at the date of last contact. If the event/censored date is more than 100 days from the start date, the patient will be considered censored at 100 days.

8.8.2.5 OVERALL SURVIVAL AT WEEK 24

The start date for overall survival at Week 24 from treatment start will be defined as the date of first exposure

Page 26 of 39

to the study drug. Death for any cause will be considered an event, with the date of death defining the event date. Patients alive at the end of the study visit will be considered censored at the date of the visit.

Overall survival at Week 24 (weeks) will be analyzed in the same way as Overall survival at Day 100 (see Section §8.8.2.4 for details).

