### 5.2 Secondary objectives

The following are the secondary objectives of this study:

- To evaluate the PD of pegcetacoplan in patients with TA-TMA.
- To evaluate the efficacy of pegcetacoplan in patients with TA-TMA.

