### 5.2.1 Secondary endpoints supporting the secondary objectives

The secondary endpoints are as follows:

• PD endpoints:

Confidential Page 29 of 89

- Absolute levels, change from baseline, and % change from baseline to Week 24 in biomarkers of complement activation: sC5b-9, C3a, C3, Bb, C4a, functional assays for classical and alternative complement pathways.
- Clinical response at Week 24, defined as improvement in laboratory markers and improvement in clinical status as follows:

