### 6.1.2 Treatment period (up to 16 weeks)

At Week 12, if a clinical and/or TMA response according to the protocol definition is not reached, the investigator may decide to continue treatment, according to his/her judgment, for a total of 16 weeks of treatment. If at Week 12 the patient has reached a partial clinical response (defined as improvement in signs/symptoms in 1 or more affected organs without meeting the protocol definition of clinical response), 4 additional weeks of pegcetacoplan every 3 days will be administered to complete 16 weeks of treatment.

At any time after the first 3 weeks of treatment, in the event of significant clinical worsening associated with active laboratory TMA (as defined in Section 6.1.2.1), the patient may be discontinued from study treatment and receive rescue therapy. In case of earlier clinical worsening, it is recommended to wait until at least 3 weeks of treatment are completed to allow pegcetacoplan to reach the target exposure and exert a clinical effect; however, if deemed by the investigator that the patient's safety is at risk, the patient can be discontinued from study treatment at any time. Discontinued patients will remain on study and will be followed for survival until the end of the study.

Any concomitant TA-TMA directed therapy will be prohibited for the entire treatment period, including plasma-exchange, defibrotide and any other complement inhibitor.

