## 6.3.3 Withdrawal of patients from treatment or study

#### 6.3.3.1 Discontinuation from treatment

A patient should be discontinued from the study treatment if, in the opinion of the investigator, it is medically necessary, or if it is the wish of the patient. See treatment stopping criteria in Section 6.1.5.

Study treatment must be discontinued if a female patient becomes pregnant.

When a patient is discontinued from treatment, the study site must immediately notify the medical monitor, the date of last IMP dose, and the date and reason for treatment withdrawal should be clearly described in the relevant sections of the eCRF. If a patient is removed from treatment because of an AE, the reason for treatment withdrawal should always be stated as 'adverse event' irrespective of whether this was the investigator's or the patient's decision.

When patients are discontinued from treatment, every effort should be made to continue their participation in the study without taking study treatment. Discontinued patients will be followed for survival until the end of the study. Patients who stop study treatment prior to the exit visit should undergo all follow-up visits and procedures through study completion, unless consent has been withdrawn (see Table 1).

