#### 6.4.9.2 Prohibited medications

Other than pegcetacoplan, any therapy for TA-TMA is prohibited during patient's participation in the study, including:

- Defibrotide.
- Any other complement inhibitor (e.g., eculizumab, ravulizumab, or narsoplimab).
- Plasma-exchange.

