## 8.3.4 Analysis related to secondary objectives

#### 8.3.4.1 Analysis of pharmacodynamics

A secondary objective is to evaluate the pegcetacoplan PD in patients with TM-TMA.

The related secondary PD endpoints are the following:

• Absolute levels, change from baseline, and % change from baseline to Week 24 in biomarkers of complement activation, which include but are not limited to sC5b-9, C3a, C3, Bb, C4a, functional assays for classical and alternative complement pathways).

PD parameters will be summarized using descriptive statistics (N, mean, standard deviation, median, minimum and maximum values).

The analysis of the PD endpoints will be performed on the PD set.

Confidential Page 63 of 89

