7.5 PHARMACODYNAMIC SET

The PD set will include all patients in the ITT set who receive IMP and have at least 1 evaluable post-dose PD measurement.

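### SAP 8.8.2.1 has no rule for complement biomarker samples taken after another complement inhibitor or plasma exchange, so the by-visit PD summaries can mix two treatments' effects

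*SAP*

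**What the plan says.** The secondary objective (Protocol 5.2) is "To evaluate the PD of pegcetacoplan in patients with TA-TMA". The endpoint (Protocol 5.2.1) is "Absolute levels, change from baseline, and % change from baseline to Week 24 in biomarkers of complement activation": sC5b-9, C3a, C3, Bb, C4a and functional assays of the classical and alternative pathways.

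SAP 8.8.2.1 summarises these by visit: "Absolute values, changes from baseline, and percent changes from baseline will be summarized. The summaries will be done on PD set". It adds individual plots over time. Protocol 8.3.4.1 is equally short: "The analysis of the PD endpoints will be performed on the PD set". Membership is decided per patient (SAP 7.5): "The PD set will include all patients in the ITT set who receive IMP and have at least 1 evaluable post-dose PD measurement". One evaluable post-dose value therefore admits all of that patient's samples, and neither document defines evaluable.

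On rescue, Protocol 6.1.2 says that after clinical worsening "the patient may be discontinued from study treatment and receive rescue therapy". It then mentions only survival follow-up for discontinued patients. Protocol 6.3.3.1 goes further: "Patients who stop study treatment prior to the exit visit should undergo all follow-up visits and procedures through study completion", unless consent is withdrawn. Table 1 marks complement biomarkers at EOT/ET, Week 20 and Week 24.

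SAP 8.8.2.2 names plasma exchange, defibrotide and complement inhibitors as prohibited medication. It counts the patient as a nonresponder at every visit after the event. TMA response and the time-to-response and duration analyses also take account of intercurrent events. The biomarker section does not.

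**The concern.** The PD summary is meant to describe what pegcetacoplan does to complement. A patient who stops it, receives another complement-directed treatment and is then sampled contributes values that reflect the other treatment, the washout of pegcetacoplan, or both. The link to the measured quantity is direct for at least one marker. Protocol 4.2 describes eculizumab as a C5 inhibitor, and Protocol 2.1 defines sC5b-9 as the soluble terminal complement complex.

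The gap also makes the SAP uneven. For response, the same treatments change how every later visit is counted; for the biomarkers, nothing happens. Protocol 6.2 says the PD assessments will help guide further development. With 12 patients, one or two individuals can visibly move a visit mean.

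**Working it through.** **The plan's own figure.** The only probability the plan computes is 72% for at least 8 responders of 12 at a true rate of 70%. The exact binomial sum over 8 to 12 responders is 0.2311 + 0.2397 + 0.1678 + 0.0712 + 0.0138 = 0.7237 (from unrounded terms), which reproduces it. It concerns response and is unaffected by this point. The plan states no figure for the biomarkers.

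**Does any text remove post-rescue samples?**
- SAP 8.8.2.1 and Protocol 8.3.4.1 contain no sample-level rule.
- SAP 7.5 works at patient level.
- SAP 8.4 concerns imputation, not removal of observed values.
- SAP 8.3 selects one record per visit window by closeness to the target day, whatever treatment the patient was then receiving.
- The intercurrent-event rule in SAP 8.8.2.2 is written for response.

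By default, then, the samples stay in. The text is silent rather than expressly retaining them.

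**Inputs for the size.** N = 12 (Protocol 8.1). The documents give neither a rescue rate nor a biomarker mean or SD, so everything below is assumed for illustration: *k* patients sampled at a visit (9 or 12), *m* of them rescued (1 to 3), and *d*, the mean percent change in rescued patients minus that in the others.

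**Formula.** Shift in the visit mean, relative to the mean of the non-rescued patients = (*m*/*k*) × *d*. Each rescued patient carries 1/12 = 8.3% of the mean when 12 are sampled and 1/9 = 11.1% when 9 are.

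**Case A: the other agent lowers the marker.** Non-rescued 0%, rescued −60%, so *d* = −60.

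| Sampled | 1 rescued | 2 rescued | 3 rescued |
|---|---|---|---|
| 12 | −5.0% | −10.0% | −15.0% |
| 9 | −6.7% | −13.3% | −20.0% |

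With post-event samples removed, the mean is 0% throughout.

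**Case B: the other agent does not lower the marker and pegcetacoplan has worn off.** Non-rescued −60%, rescued 0%, so *d* = +60.

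| Sampled | 1 rescued | 2 rescued | 3 rescued |
|---|---|---|---|
| 12 | −55.0% | −50.0% | −45.0% |
| 9 | −53.3% | −46.7% | −40.0% |

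With post-event samples removed, the mean is −60%. The shift has the same size and the opposite sign.

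**Median.** In both cases the rescued patients are a minority at one extreme and the others share one value, so the median equals the non-rescued value. Real data have spread, so the median could move, but by less than these means suggest.

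**Time since last dose.** Treatment ends at Week 12 or Week 16 for completers. Scheduled Week 24 is therefore 24 − 16 = 8 to 24 − 12 = 12 weeks after the last dose. The endpoint's final visit is off drug even without rescue, and the by-visit summary does not separate it from on-drug visits.

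**The case against.** The strongest reply is that this is a 12-patient descriptive pilot with no hypothesis tests, and that much of the distortion would be visible. SAP 8.1 reports median, quartiles, minimum and maximum beside the mean. Individual biomarker plots, counts of intercurrent events by category and full listings are planned. PK is sampled at the same late visits, so loss of drug could be seen alongside the PD value. All this stands and limits the harm. It does not tell a reader of the summary table which values followed another treatment, and no marking of event dates on the plots is planned.

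Some stronger readings are tempting, but the documents do not support them:

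- *The bias always favours the drug.* The panel includes C3, C3a, Bb and C4a as well as sC5b-9, and Protocol 4.2 places pegcetacoplan at C3 and eculizumab at C5. Markers that the other agent does not lower may drift back once pegcetacoplan stops, as in Case B.
- *About 3 of 12 patients will be rescued.* The estimate that 9 complete 4 weeks covers loss for any cause. Clinical worsening is defined narrowly: active laboratory TA-TMA plus 3 of 5 organ injuries.
- *Suppression at Week 24 in a rescued patient can only come from the other treatment.* Recovery from the disease, or management of triggering conditions, could also lower markers from a baseline taken in active TA-TMA.

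Post-rescue sampling is not settled either. Protocol 6.1.2 speaks of survival follow-up, while 6.3.3.1 speaks of all visits and procedures. Protocol 6.1.2 bans other TA-TMA therapy for the treatment period, while 6.4.9.2 bans it throughout participation. These passages must be reconciled.

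Finally, dropping post-event values has its own bias: late visits would then over-represent patients who did not need rescue. That is a fair objection to exclusion alone.

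**Conclusion.** The point holds as a gap in specification. Followed as written, the plan puts samples taken after another complement inhibitor or plasma exchange into summaries intended to describe pegcetacoplan's PD. It gives no means of separating them in the tables. Excluding them later by interpreting evaluable would be a post hoc choice in an open-label study.

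The consequence requires at least one rescued patient with later samples. Its direction depends on the marker: overstated suppression where the other agent lowers it (sC5b-9 under C5 blockade), possible dilution where it does not. Its size cannot be derived from the documents. Under the assumed 60-point difference, 1 to 3 rescued of 9 to 12 sampled move the mean by 5 to 20 points, and the median may stay put. This affects a secondary, descriptive endpoint; it changes no sample size and no response result. The change is worth making because it is cheap and makes the PD result interpretable.

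**What to change.** In SAP 8.8.2.1:

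1. Define the main by-visit PD summary as values dated before the patient's first prohibited complement inhibitor or plasma exchange, taken from the medically reviewed list in SAP 8.8.2.2.
2. Keep the all-sample summary as supportive.
3. Report the number of post-event samples at each visit.
4. Mark the event date and the last pegcetacoplan dose in the listings and individual plots.
5. Show samples taken on pegcetacoplan separately from those taken after the last dose, the latter by weeks since last dose.

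Separately, reconcile Protocol 6.1.2 with 6.3.3.1 on which procedures continue after discontinuation, and with 6.4.9.2 on how long other TA-TMA therapy is prohibited. The analysis then rests on a known sampling plan and a clear event definition.

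The cost is about a paragraph of SAP text, reuse of dates already needed for the response analysis, and one more set of tables. The main summary will have fewer values at late visits and will lean toward patients who were not rescued, which is why the all-sample version stays beside it.

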### 6.1.1 Screening period (up to 2 weeks)

Informed consent will be obtained at screening before any study-related procedures being conducted. Patients will be screened to confirm that the patient selection criteria for the study have been met. Key inclusion and exclusion criteria will be reviewed by the study medical monitor and eligibility will be confirmed prior to the enrollment.

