# 6.2 Discussion of study design

This study will be the initial exploration of pegcetacoplan in patients with TA-TMA. The assessments of the PK, PD, safety and efficacy following administration of induction doses followed by s.c. maintenance doses will guide decisions to further develop the drug.

The proposed inclusion criteria of the study will ensure that only patients who have not responded to first-line management of TA-TMA including withdrawal or minimization of medication insult to endothelium such as immunosuppressants and treatment of co-existing conditions such as infections and GVHD are enrolled.

Measures will be taken to minimize risk to participants in this study, including recommendation for vaccination against encapsulated pathogens, mandatory administration of prophylactic antibiotics and measurement of antibodies, apart from standard safety assessments.

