# 6.3 Selection of study population

#### 6.3.1 Inclusion criteria

A patient must fulfill the following criteria in order to be included in the study:

- 1. Male and female patients aged  $\geq$  18 years at the time of ICF signature.
- 2. Received allogeneic HSCT from a related or unrelated, human leukocyte antigen-matched or mismatched donor. Patients having received any of the following stem cell sources are eligible: granulocyte colony stimulating factor mobilized peripheral blood stem cells, bone marrow, umbilical cord blood.
- 3. Diagnosis of TA-TMA established as per the laboratory markers below, indicating TMA:
  - a. De novo or progressing thrombocytopenia (platelet count  $< 50 \times 10^9/L$  or > 50 % decrease in platelet count from the highest value achieved after transplantation). AND
  - b. Elevated LDH (> 1.5 x ULN).

AND at least 2 additional laboratory/clinical criteria among the following:

- c. Presence of schistocytes on the peripheral blood smear (≥ 2 per hpf) or histologic evidence of microangiopathy in any biopsied organ. OR
- d. De novo anemia (hemoglobin < LLN or anemia requiring PRBC transfusion support as per local institutional standard). OR
- e. Proteinuria (random urinalysis protein concentration  $\geq 30$  mg). OR

Confidential Page 35 of 89

- Clinical Study No: Sobi.PEGCET-201
- f. Elevated plasma concentration of sC5b-9 above ULN. OR
- g. Arterial hypertension, defined by systolic BP ≥ 140 mmHg and/or diastolic BP ≥ 90 mmHg.
- 4. Have a diagnosis of TA-TMA that persists despite initial management of any triggering condition.
- 5. Have a rUPCR  $\geq 1$  mg/mg.
- 6. Women of childbearing potential, defined as any women who have experienced menarche and who are NOT permanently sterile or postmenopausal, must have a negative serum pregnancy test at screening and agree to use protocol-defined methods of contraception for the duration of the study and 8 weeks after their last dose of IMP.

Note: Postmenopausal is defined as having had 12 consecutive months with no menses without an alternative medical cause.

- 7. Men must agree to the following for the duration of the study and 8 weeks after their last dose of IMP:
  - a. Avoid fathering a child.
  - b. Use protocol-defined methods of contraception.
  - c. Refrain from donating sperm.
- 8. Patient and/or legally authorized representative must be capable of giving signed informed consent, which includes compliance with the requirements and restrictions listed in the ICF.

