#### 6.5.7.3 Overall survival, time to response, duration of response, TA-TMA relapse

Overall survival will be assessed at Day 100 from the day of TA-TMA diagnosis and at Week 24 from treatment start. The day of TA-TMA diagnosis will be defined as the earliest date when all required laboratory criteria outlined in Inclusion Criterion #3 are met. Date of death and reason for death will be collected (whether related to TA-TMA or not).

Time to clinical/TMA response will be measured from the time of first IMP dose to the first documentation of attainment of a clinical or of a TMA response as defined in Section 5.2.1. Duration of clinical and of TMA response will be measured from the first documentation of attainment of a response until TA-TMA relapse.

Confidential Page 58 of 89

[figure not shown]
Pegcetacoplan/TA TMA

Clinical Study No: Sobi.PEGCET-201

TA-TMA relapse will be defined as reappearance of all laboratory markers as outlined in Inclusion Criterion #3 in a patient who has reached a clinical response.

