#### 8.3.4.2 Analysis of secondary efficacy endpoints

The secondary efficacy endpoints are described in Section 5.2.1.

A secondary endpoint is clinical response at 24 weeks. A composite estimand is used where patients meeting intercurrent events are considered as failures. The intercurrent events of interests are use of prohibited medication or study withdrawal before Week 24. Patients meeting these intercurrent events will be considered as failures/nonresponders.

A 2-sided 95 % confidence interval for the proportion will be calculated using the Clopper-Pearson method.

Clinical response at Week 12 as well as TMA response at Week 12 and Week 24 will be evaluated the same way as clinical response at Week 24.

Another secondary endpoint is overall survival at Day 100 from diagnosis of TA-TMA. Pegcetacoplan withdrawn patients for which survival at Day 100 is unknown will be censored at the date of last contact. Kaplan-Meier curve estimates of survival at Day 100 and survival curves will be estimated.

Overall survival at Week 24 from study Day 1 will be evaluated the same way as overall survival at Day 100 from diagnosis of TA-TMA.

Time to clinical response will be defined as the time from study Day 1 to first occurrence of clinical response and will be evaluated for:

- Patients achieving clinical response (without a preceding ICE) at any time during the study.
- Patients achieving clinical response at Week 24 without meeting an ICE.

Time to clinical response will be analyzed using Kaplan-Meier methodology. Kaplan-Meier curves and estimates will be presented.

Time to TMA response will be evaluated in the same way as time to clinical response.

Duration of clinical response is defined as the time from the first observed clinical response until the response criteria is no longer fulfilled or until end of study. Duration of response will be defined for patients with clinical response without meeting an ICE. Duration of clinical response will be analyzed using Kaplan-Meier methodology. Kaplan-Meier curves will also be presented.

Duration of TMA response will be evaluated the same way as duration of clinical response.

TA-TMA relapse at Week 24 will be defined for patients reaching clinical response at some point of the study. Counts and proportions of patients with and without relapse at Week 24 will be summarized.

The analysis of the secondary endpoints will be performed on the ITT set.

Confidential Page 64 of 89

Pegcetacoplan/TA TMA

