7.3 INTENT-TO-TREAT SET

The intent-to-treat (ITT) set will include all patients enrolled. This analysis set will be used for efficacy endpoints. ITT should be identical to the Safety set, i.e. all enrolled patients who received at least one dose of IMP. Enrolled patients are defined as Informed Consent Form (ICF) signed and all eligibility criteria are met.

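### Day-100 survival is an ordinary Kaplan-Meier from TA-TMA diagnosis in patients who enter the analysis only later, so it is conditional on survival to entry and should be labelled as such

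*SAP*

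**What the plan says.** **Estimator and time origin.** SAP 8.8.2.4 reads: "Overall survival at Day 100 (days) is defined as survival from the day of TA-TMA diagnosis and will be analyzed using Kaplan-Meier model". It reports the Day-100 estimate with its 95% CI and the curves, "together with estimates of median and quartiles obtained from the model". Its other rules concern right-censoring only: at last contact, or at 100 days if the event or censoring date falls later. Protocol 8.3.4.2 uses the same method: "Kaplan-Meier curve estimates of survival at Day 100 and survival curves will be estimated".

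**Day zero.** Protocol 6.5.7.3: "The day of TA-TMA diagnosis will be defined as the earliest date when all required laboratory criteria outlined in Inclusion Criterion #3 are met". This date can precede consent.

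**Who is analysed.** Efficacy uses the ITT set. Protocol 8.2.3 defines it as all patients enrolled. SAP 7.3 repeats that and adds: "ITT should be identical to the Safety set, i.e. all enrolled patients who received at least one dose of IMP". The same SAP section then defines enrolled as consent signed and all eligibility criteria met.

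**What happens between day zero and entry.** Inclusion criterion 4 (protocol 6.3.1) requires patients to "Have a diagnosis of TA-TMA that persists despite initial management of any triggering condition", and protocol 6.1.1 allows up to 2 weeks of screening. No criterion in 6.3.1 or 6.3.2 limits the time since diagnosis.

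**What is reported nearby.** SAP 8.7.2 summarises time from diagnosis to enrollment as a baseline variable. SAP 8.8.2.5 reports survival to Week 24 from first exposure.

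**The concern.** A patient who dies after diagnosis but before entering the study is never in the analysis, yet each analysed patient's days between diagnosis and entry are counted as days at risk of death. This is left truncation that the analysis does not handle. The result is survival to Day 100 given survival to entry, under a name that says survival from diagnosis.

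The Day-100 cap adds an extreme case. A patient first dosed more than 100 days after diagnosis would count as a certain Day-100 survivor while contributing no treated time before Day 100.

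What is at stake is interpretation. In a single-arm study, a survival figure is naturally read against outside figures, such as the mortality of up to 60% to 75% cited in protocol 4.1. Part of the Day-100 figure would reflect how late patients entered. Protocol 6.2 says the efficacy assessments, together with PK, PD and safety, will guide further development.

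**Working it through.** **The plan's own figures.** Neither document gives an expected Day-100 survival or an expected gap. The only design probability is 72% for at least 8 responders of 12 at a true rate of 70% (protocol 8.1, SAP 5). The exact binomial tail is 0.7237, so it reproduces, but it concerns response, not survival. Everything below is therefore illustrative.

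**Inputs.** n = 12 (protocol 8.1). True Day-100 survival S of 0.25 to 0.40 is an assumption: it is the complement of the 60% to 75% mortality in protocol 4.1, which has no time point. The gap g from diagnosis to entry is assumed to be 7, 14 or 28 days.

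**Formula.** If every patient enters at day g, ordinary Kaplan-Meier from diagnosis estimates S(100)/S(g). With a constant hazard, S(t) = S^(t/100), so the estimate is S^(1 − g/100).

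| Gap | True 40% | Excess (points) | True 25% | Excess (points) |
|---|---|---|---|---|
| 7 days | 0.40^0.93 = 0.4265 | about 2.6 | 0.25^0.93 = 0.2755 | about 2.6 |
| 14 days | 0.40^0.86 = 0.4547 | 5.5 | 0.25^0.86 = 0.3035 | 5.4 |
| 28 days | 0.40^0.72 = 0.517 | 11.7 | 0.25^0.72 = 0.369 | 11.9 |

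**Median.** The true median is 100 × ln 2 / (−ln S): 75.6 days at S = 0.40 and 50.0 days at S = 0.25. Ordinary Kaplan-Meier shifts it by the gap, so 14 days gives 89.6 and 64.0 days.

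**Sensitivity to the assumptions.**
- If deaths cluster early (Weibull shape 0.7, true 40%), the estimates at 7, 14 and 28 days are 0.461, 0.504 and 0.583, so the excess is larger.
- If the comparator is also required to survive until persistence is established on day p, its survival is S^(1 − p/100) and the excess shrinks. With p = 3 and g = 7 it is 0.4265 − 0.4111, or 1.5 points. With p = 7 and g = 14 it is 0.4547 − 0.4265, or 2.8 points.

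**Scale.** With 5 of 12 alive, the exact 95% CI is 15.2% to 72.3%.

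**Delayed entry at n = 12, no treatment effect** (20,000 simulated trials, constant hazard, uniform gap):

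| Gap | True S | Ordinary: mean (RMSE) | Delayed entry: mean (RMSE) | Delayed entry falls to 0% despite survivors |
|---|---|---|---|---|
| 0–14 days | 0.40 | 0.425 (0.145) | 0.402 (0.151) | 1.0% |
| 0–14 days | 0.25 | 0.276 (0.131) | 0.253 (0.131) | 1.6% |
| 0–28 days | 0.40 | 0.456 (0.155) | 0.407 (0.163) | 2.1% |
| 0–28 days | 0.25 | 0.305 (0.145) | 0.258 (0.138) | 2.8% |

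**Delayed entry if dosing halves the hazard** (assumed untreated Day-100 survival 25%; the target is survival from diagnosis including deaths before dosing):
- Gap 0–14 days: target 47.7%, ordinary 52.6%, delayed entry 50.4%. The bias falls from 4.9 to 2.7 points; RMSE is 0.152 ordinary against 0.158 delayed.
- Gap 0–28 days: target 45.4%, ordinary 54.8%, delayed entry 50.6%. The bias falls from 9.4 to 5.2 points, with no gain in RMSE.

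Delayed entry therefore removes most of the bias only if treatment has no effect. If dosing halves the hazard, it removes about half.

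**The case against.** The strongest case against has four parts.

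**Much is already disclosed.** The time origin is explicit, time to enrollment is summarised, and Week-24 survival starts at first dose. This stands in part. A careful reader could infer the conditioning, but neither document states it. Time to enrollment is not time to first dose and is not linked to the survival estimate. The Week-24 result does not correct the Day-100 curve, median or quartiles.

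**No outside comparison is planned.** The analysis is descriptive, with no test, threshold or benchmark, and the mortality in protocol 4.1 has no time point. This stands, and it limits the consequence to interpretation.

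**The gap may be short.** Protocol 6.5.5.2 lets local laboratory results support a rapid start, and Table 1 footnote p foresees screening samples on the day before first dose. This also stands, but no ceiling is given.

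**Delayed entry is not clearly better at n = 12.** Its RMSE is equal or worse in three of the four no-effect scenarios, and it uses only time after entry. This stands, and it is why delayed entry should not replace the planned estimate.

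Two stronger readings are tempting. A reader might infer that the figure must overstate survival relative to all diagnosed patients. The documents do not support that, because enrolment also selects persistent disease: protocol 6.2 says the criteria admit "only patients who have not responded to first-line management of TA-TMA". The net direction against all diagnosed patients is unknown. A reader might also infer that no analysed death can precede first dose. SAP 7.3 expects that, but protocol 8.2.3 and the SAP's own definition of enrolled leave room for a patient who is eligible, undosed and in the ITT set.

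**Conclusion.** The point holds as a labelling and interpretation problem. The Day-100 estimate, curve, median and quartiles are conditional on survival to entry and are biased upward as survival from diagnosis in comparable patients. The mechanism follows from the documents; the size does not, because the gap is not given. The illustrated excess of about 2.6, 5.5 and 12 points for gaps of 7, 14 and 28 days rests on a constant hazard, a common gap and true Day-100 survival of 25% to 40%. It would be larger if deaths cluster early and smaller against a comparator already selected for persistence. At n = 12, sampling error exceeds all of these shifts, but the confidence interval does not account for the bias.

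This is one of eleven secondary efficacy endpoints, all descriptive. No error rate or decision rule is affected. The change should be made because it is cheap, not because the study's conclusions depend on it.

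**What to change.** Amend SAP 8.8.2.4 before database lock, and date the change, because SAP Section 10 already describes recruitment in the past tense.

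1. Keep the ordinary Kaplan-Meier, but label it *conditional on survival to first dose, not survival from diagnosis*. Show the distribution of time from diagnosis to first dose beside it. This is the minimum fix.
2. Add a supplementary delayed-entry Kaplan-Meier with time zero at diagnosis, numbers at risk and the earliest entry day stated. Patients enter at first dose, or at enrollment if any enrolled but undosed patient is in the ITT set; in that case, adapt the label in item 1. List patients who entered after Day 100 as not contributing.
3. State the limits of the supplement. It assumes that entry time is independent of prognosis, applies to persistent TA-TMA only, and uses time after entry only. If treatment has an effect, it describes patients treated from the earliest entry day and removes only part of the bias.

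Showing both estimates in all cases avoids a choice that depends on the data.

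**Cost.** One SAP paragraph, one derived variable and an entry in SAP Section 10 for the added analysis. All dates are already collected. The downside is a less stable supplementary estimate: RMSE is similar or slightly worse in most scenarios, and it falls to 0% despite survivors in about 1% to 3% of simulated trials.
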